1 PROTOCOL SUMMARY

1.1 SCHEMA

Prior to Enrollment (21 month Recruitment Period)

Total 234: Screen potential participants by inclusion and exclusion criteria, obtain informed consent, Assign Study ID number

Randomize on REDCap (done by local coordinator)

KiT intervention arm (117 participants)

Control arm (117 participants)

Baseline

Local coordinator: securely transfer Memotext Study ID, Randomization arm and phone number of newly randomized participant. Memotext to activate enrollment by sending start-text to participants in **both arms**

Local coordinators: Collect HbA1c lab-reported value no later than 6 months prior to enrolment date, emergency department and hospitalization data, and OHIP/RAMQ numbers to link to admin data

Memotext: sends SMS of baseline questionnaires as URLs that linkout to REDCap for: KiT demographic Survey ,READDY, BDA Stigma Subscale, and SEDM **to both arms**

Intervention Start

Memotext: based on READDY tool responses, sends SMS of T1D-related questions, support, and management **to only intervention arm for 12 months. Both groups receive usual medical care during intervention period.**

6-Month

Follow-up assessments: Memotext sends SMS of 6-month questionnaires as URLs that linkout to REDCap: KiT Survey, READDY, BDA Stigma Subscale, SEDM **to both arms.** Interim Process Evaluation with intervention arm

12-Month

KiT intervention modification: based on results of process evaluation; adjustments or modification to KiT algorithm will be made to improve message and content delivery, and improve user engagement and satisfaction

Final Follow-up assessments: Memotext sends SMS of 12-month questionnaires as URLs that linkout to REDCap: KiT Survey,READDY, BDA Stigma Subscale, and SEDM **to both arms.** Process Evaluation, Health System utilization and Cost of implementation analysis performed at end of intervention.

1.2 SCHEDULE OF ACTIVITIES (SOA)

Table 1: Schedule of activities for KiT intervention

Time Point	Enrolment/ Randomization (21 month randomization period)	Intervention Period (12 months)				End of intervention
	-1 week	0	3 months	6 months	12 months	
ENROLMENT						
Eligibility screen	X					
Informed consent	X					
Randomization	X					
INTERVENTION*						
Active arm		X	X	X	X	
Control arm						
ASSESSMENTS						
KiT						
Demographics survey		X		X	X	
READY		X		X	X	
SEDM		X		X	X	
Barriers to Diabetes Adherence (BDA) in Adolescence Stigma subscale		X		X	X	
T1D-related hospitalization (OHIP/RAMQ)					X	
T1D-related ED visits (OHIP/RAMQ)					X	
Process Evaluation			X	X	X	
KiT modifications**			X	X		
Cost of implementation analysis			X	X	X	

*only participants in the active arm will receive the KiT intervention during the 12-month intervention period. Both study arms will receive usual medical care during 12-month intervention period.

**will occur in real-time and only if results of process evaluation reveal modifications or adjustments are required to improve user engagement and satisfaction

2 INTRODUCTION

2.1 STUDY RATIONALE

During the transition to adult diabetes care, young adults with type 1 diabetes (T1D) are at risk for deterioration of their diabetes management, having a gap in establishing adult care, and of acute life-threatening complications such as diabetic ketoacidosis. We have shown that there are persistent gaps in transition care services, poor uptake of existing transition resources, and gaps in collaboration and linkages between pediatric and adult diabetes providers. Most digital transition interventions do not offer personalized educational content or resources to support patients based on their stage of transition readiness and they require additional human resources. As a result, existing digital interventions do not adequately engage patients across the transition continuum or demonstrate scalability. *Our study proposes to implement and evaluate a pragmatic digital tool that delivers just-in-time personalized transition education, to improve patient-reported diabetes outcomes and gaps in diabetes care.*

2.2 BACKGROUND

Type 1 diabetes (T1D) is one of the most common chronic diseases of childhood with significant morbidity and mortality(1). A particularly challenging period for people living with type 1 diabetes (T1D) is emerging adulthood (18-30 years) when parental involvement in diabetes care is decreasing and emerging adults are undergoing emotional, physical, financial, occupational, and social changes within a short period of time(2-4). Prevention of T1D-related complications is vital for patient health.

Randomized trials have demonstrated the importance of optimizing blood sugar control (glycemic control) in preventing chronic complication(5,6). However, data from a large U.S. type 1 diabetes registry demonstrated that glycemic control deteriorates in adolescence and remains suboptimal throughout the early to mid-20s(7). This is particularly worrisome because glycemic control early in life has a lasting effect on the future risk of developing long-term diabetes complications(5,6). Further, nearly one in three U.S. adolescents and emerging adults with T1D already have diabetes complications (retinopathy, neuropathy, and nephropathy)(8,9). Prevention of acute diabetes-related complications are equally important. Shulman et al. found that emerging adults with diabetes in Ontario have a 4.27 times higher risk of death compared with those without diabetes (95% CI 3.37 to 5.41)(10).

From pediatric to adult diabetes care: The incidence of type 1 diabetes (T1D) in Canada is amongst the highest in the world (1). In 2012, there were 6,676 children under 18 years of age living with T1D in Ontario alone(11). As these children enter emerging adulthood, they face challenges that complicate the transition to adult diabetes care. One single-centre study in the United States found that 34% of T1D patients transitioning to adult programs reported a gap of more than 6 months in establishing adult care(12). Using data from Ontario, we showed that almost half of emerging adults with T1D had a gap exceeding 12 months between their last pediatric appointment and the time they saw their eventual adult diabetes care physician(13). This may be due to a number of recognized barriers for emerging adults, including making a connection with the new adult team, difficulties communicating with the new clinic regarding scheduling appointments, and lack of perceived value in the clinic visit(14). Many emerging adults arrive at adult clinics feeling inadequately prepared for transition and are often not counselled on topics relevant to their specific needs. Feeling unprepared for adult care has been associated with an increased risk of having a gap of more than 6 months between pediatric and adult care(15). Further, we have shown that the struggles that transitioning T1D patients experience in taking on multiple new responsibilities and adult providers' lack of appreciation of these struggles are key barriers to successful transition. We have also found that upon the transfer to adult care there was often no sharing of a formal medical summary(16). These studies have identified the need for improved transition preparation, care coordination, and communication between pediatric and adult providers(15). We have shown that there is

variability in transition practices across Ontario pediatric diabetes centres(13). There is an urgent need to develop a system-level innovative approach to help emerging adults remain engaged in their care during this vulnerable period.

To reduce complications, the medical care of emerging adults with T1D requires regular access to specialized healthcare services. However, during the transfer to adult care emerging adults are at high risk of dropping out of medical care altogether(17–19), only to resurface with life-threatening diabetes-related complications such as diabetic ketoacidosis (DKA)(20–22). The goal of transition care is to provide care that is uninterrupted and developmentally appropriate while developing adolescents' and emerging adults' skills in decision-making and self-care(20). However, we have documented significant variability and deficiencies in transition care services. In Ontario, pediatric diabetes centres reported challenges related to transition preparation, communication with adult teams, adult programs' ability to meet the needs of emerging young adults, and loss to follow-up(13). We have also found a lack of transition care services in pediatric diabetes centres across Quebec. Adult diabetes care providers in Quebec perceive an absence of transition care preparation for adult care as a major barrier to successful transition(16,23). A few studies have addressed this lack of transition care services using digital resources, but they did not offer personalized educational content or resources to support patients based on their stage of readiness to transition and they required additional human resources. They also failed to fully address the range of factors influencing transition, including the complex psychosocial issues that determine ongoing engagement and glycemic control in this age-group. As a result, existing digital interventions do not adequately engage patients across the transition continuum or demonstrate scalability(24).

Interventions: A variety of interventions targeting the transition from pediatric to adult T1D care have been evaluated, including those directed at patients (educational programs, skills training), clinic staff (transition coordinators, joint clinics run by pediatric and adult physicians), and services (separate young adult clinics, out of hours phone support, enhanced follow-up)(25–33). However, these models tended to be institution-specific with limited access (i.e. location within academic hospital-based sub-specialty centres or targeted 'young adult' clinics), particularly for those living away from home attending post-secondary school or those living outside urban centres. Although these interventions show promise, they are limited by their cost, scalability, and generalizability.

Digital Tools for Transitioning Youth: Most digital interventions for supporting T1D self-management do not focus on providing personalized transition support resources, and do not facilitate content delivery that is specific to the individual's stage of transition readiness or on expressed topics of interest, and require additional human resources (24). As a result, existing digital interventions have not demonstrated cost effectiveness, scalability, or the ability to adequately engage patients across the transition continuum(24).

For example, the Maestro Project in Manitoba demonstrated that a system navigator model that connected transitioning patients to adult care improved the drop-out rate of adult medical care(29). However, this program did not see any improvements in short term outcomes or evaluate the scalability and economic impact of the program. Another study testing a system navigator approach found that clinic visits were maintained, diabetes control improved, and DKA rates reduced. This study infers that the navigator had a significant role in improving outcomes, however, it does not address the relationship between the patient and their pediatric and adult providers over the transition period(32). Our digital tool will help youth with T1D learn more information about the adult diabetes center they've been referred to as we will be providing a link via a text message to KiT, that will take participants to a landing page that is specific to their adult referral site and will have information about the clinic's healthcare providers, clinic address and contact information, and who to contact to schedule or change appointments, and information on any special programs offered to this patient population.

While telemedicine is being explored as a modality for improving communication and accessibility across the transition period, it remains limited by the lack of interoperability with health records, the personalization of technology used, and reimbursement for the services delivered(24). Recognizing these implementation challenges, the use of text messaging or SMS is being explored as an engaging, acceptable, accessible, and cost-effective way of reaching patients(34). Interestingly, all text message studies to date have relied on a health care provider to deliver the content to patients, or they default to simple reminders for self-care(34,35). To our knowledge, our proposed intervention will be the first to explore how to develop a text message-based algorithm designed to assess the patient's diabetes status, and provide personalized resources associated to that status. Recognizing that most adolescents with poor glycemic control turn to technology in a reactive manner, we hypothesize that pushing support content based on quick and simple assessments via SMS, over time, may improve engagement with support content and self-management(24).

While we have strong evidence of the short and long-term benefits of intensive glycemic control, most adolescents and emerging adults living with T1D are unable to achieve glycemic targets. There are many barriers to optimal T1D transition care, involving a range of patient, provider, and health system factors. Patient-related barriers include limited knowledge and skills for diabetes self-management, competing priorities (e.g. family/school/social relationships), and difficulty making a connection with the adult team. There are also a number of provider- and system-related barriers, such as incomplete transfer of patient information between pediatric and adult providers and poor uptake of available structured tools into practice(36).

2.3 RISK/BENEFIT ASSESSMENT

The value of the information to be gained from this study outweighs the risks of participation in the study as we do not expect the KiT intervention to cause any negative effects on participants, and previous research has already demonstrated that personalized support and data collection must result in meaningful feedback or provide support to the patient(37). The KiT intervention can deliver all of these features and will be delivered through a medium that is used by adolescents on a daily basis, mobile phones and text messaging. This makes this intervention more likely to be acceptable to users. There is a potential risk of users finding the KiT text messages intrusive or bothersome. To minimize this risk, we will be offering user options to customize frequency and time of delivery of texts. In addition, there is a potential risk of personal data being revealed due to the nature of how this intervention is delivered – via text-messaging. However, Memotext will never ask participants any personal identifying information, nor will Memotext receive any personal identifying information from the study team, apart from the participant phone number and Study ID number; both needed to onboard and activate the participant with the KiT intervention. Participants will also be briefed during the consent and enrollment process to ensure that their mobile device is their own personal device and is not shared with anyone else (friend or family), and that they should not text KiT any personal identifying information so as to minimize the risk of loss of confidentiality and privacy. Furthermore, KiT will be hosted on a secure sever at Memotext offices in Toronto; these servers will be encrypted and will not be accessed by any members outside of the Memotext research team, increasing protection of privacy and confidentiality. Overall, this intervention has the potential to offer the missing support and resources needed for young adults as they prepare to transition from pediatric to adult diabetes care, and this support will be offered in a private and confidential manner.

3 OBJECTIVES AND ENDPOINTS

The **primary objective** of this study is to compare the effectiveness of a text message-based T1D transition intervention that will personalize transition education and support, as an adjunct to usual T1D transition care versus usual transition care alone on a patient-reported outcome measures (PROM) called the Self-Efficacy for Diabetes Management (SEDM) scale, measured at baseline, 6 months, and 12 months after enrollment in the study.

The **secondary objectives** of this study are to evaluate the impact of this text-messaging based intervention on:

- other patient reported experiences and outcomes (PREMs/PROMs) including the READY tool, a transition readiness assessment for emerging adults with diabetes diagnosed in youth; and the Barriers to Diabetes Adherence in Adolescence (BDA) questionnaire Stigma Subscale for assessing perceived stigma
- self-reported time between final pediatric diabetes visit and first adult diabetes visit
- self-reported and/or lab reported A1c at baseline and at 12 months after enrollment to study (depending on data availability)
- diabetes-related ED visits (measured using self-reported, medical chart and health administrative data)
- diabetes-related hospitalizations (measured using self-reported, medical chart and health administrative data)
- Aggregate and direct medical costs associated with the intervention and its implementation study data and administrative data)
- Exploring how the KiT large language model (LLM) chatbot is used in a real-world setting for more natural conversations and opportunities for us to improve its performance over time. The LLM chatbot is not a learning model and will only utilize existing resources gathered for the KiT study.

An additional secondary, exploratory objective is to conduct an **embedded process evaluation**. The process evaluation will occur during the delivery of the intervention, real-time engagement metrics will be analyzed to evaluate participant engagement and will allow for intervention modification to increase and improve user engagement and content delivery. The objectives of the process evaluation are to evaluate how and why the intervention achieved (or failed to achieve) the desired effects in order to gain an in-depth understanding of whether the intervention was received as intended, the mechanisms of action, and the conditions and factors associated with initial engagement and sustained use of the intervention. Additionally, we would like to identify the different paths of engagement (i.e., combinations of KiT components) that produce a positive effect on trial outcomes. Overall, the embedded process evaluation will optimize the engagement with the intervention and assess the feasibility of implementing this intervention in the real-world.

OBJECTIVES	ENDPOINTS	JUSTIFICATION FOR ENDPOINTS
Primary		
Compare the effectiveness of a digital T1D transition platform that will personalize transition education and support, as an adjunct to usual T1D transition	Self-efficacy for diabetes management measured by the Stanford self-efficacy for Diabetes Management scale (SEDM) at baseline, 6 months, and 12 months. The SEDM is an 8-item measure answered on a Likert scale from 1 (not at all confident) to 10 (totally confident), how confident they feel that they can carry out the listed tasks regularly at the present time. The	Validated and reliable ($\alpha = 0.90$); shown to have good internal consistency and test-retest validity; measure used in adolescents with type 1 diabetes(38,39); measure of self-efficacy related to core elements of diabetes self-management in

OBJECTIVES	ENDPOINTS	JUSTIFICATION FOR ENDPOINTS
care versus usual transition care alone on diabetes self-efficacy	score is calculated using the mean of the eight items with higher scores indicating self-efficacy. Minimal clinically important difference is 10%	adolescents with type 1 diabetes
Secondary		
evaluate the impact of this text message-based intervention on the following, compared to the usual transition care alone: 
 • Transition readiness • perceived stigma of living with T1D • self-reported time between final pediatric diabetes visit and first adult diabetes visit • self-reported and/or lab reported A1c at baseline and at 12 months after enrollment to study (depending on data availability) • diabetes related ED visits • diabetes related hospitalization • Cost of implementation • Explore how the KiT LLM chatbot is used in a real-world setting for more natural conversations and opportunities for us to improve its performance over time. The LLM chatbot is not a learning model and will only utilize 	
 • transition readiness measured by the READDY tool at baseline, 6 and 12 months; READDY is a transition readiness assessment for emerging adults with diabetes diagnosed in youth. The READDY tool assesses diabetes-related knowledge or skill items by querying respondents on 42 total items split into 5 domains: knowledge, navigation, health behaviors, and insulin pump skills. Respondents answer on a Likert scale from “yes, I can do this” to “Haven’t thought about it”; confidence level is evaluated in each domain • the Barriers to Diabetes Adherence in Adolescence questionnaire (BDA) Stigma Subscale; in our study, stigma will be defined as an affirmative response to at least one of three key items on this subscale • A1c collected at baseline and 12 months after enrollment to study will be self-reported and/or lab-reported (depending on data availability) • Diabetes related ED visits, hospitalizations, will be measured for the 12 months prior to and 12 months during the intervention using self-reported, medical chart, and health administrative data from ICES. • Costs of implementation • LLM chatbot data 	
 • The READDY tool has been validated during its development by examining its correlation with existing validated transition readiness tools such as TRAQ(40); the READDY tool was favored by the KiT subcommittee that included a patient partner. The KiT subcommittee felt that compared to other transition readiness scales specific to diabetes, the READDY tool was specific and relevant to what is being evaluated and it is patient-reported • the Barriers to Diabetes Adherence in Adolescence questionnaire was developed to measure psychosocial barriers to adherence in adolescents with T1D; the stigma subscale has previously shown to be useful in research and clinical settings(41) • HbA1c: From long-term follow up of the landmark Diabetes Control and Complications Trial (DCCT) participants, early metabolic control has a lasting legacy. Individuals randomized

OBJECTIVES	ENDPOINTS	JUSTIFICATION FOR ENDPOINTS
existing resources gathered for the KiT study.		
to intensive therapy experienced a reduced risk of retinopathy up to 10 years after the study ended despite the convergence of mean HbA1c values to similar levels in both groups (~8%)(42). This underscores the importance of good metabolic control in early adulthood to prevent future diabetes complications. Further, HbA1c is at its highest (indicating poorest control) in the 18-24 year age group(7), even stabilizing HbA1c during this time would indicate a clinical improvement from the current state.
 
 • Cost of implementation will be collected to ascertain the cost of developing and using this intervention in a hospital setting in Ontario and Quebec; variables that will be collected for this analysis will include: salaries for staff working on the design, development and management of the intervention for the entire intervention duration; salary of research coordinators working to onboard participants to the intervention; cost of digital services and office equipment needed to develop and manage the intervention

OBJECTIVES	ENDPOINTS	JUSTIFICATION FOR ENDPOINTS
		(computers, hosting service, servers); cost of REDcap servers and hospital IT support for REDCap integration with MEMOTEXT platform
Exploratory		
Evaluation of participant engagement and intervention fidelity	Embedded process evaluation using real-time engagement metrics (i.e. number of participants who are engaging with intervention messages on and which types of messages are the most and least engaged with, identify the different paths of engagement (i.e., combinations of KiT components) that produce a positive effect on trial outcomes).	Concurrent process evaluation allows for real-time intervention modification to increase and improve user engagement and content delivery

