3.1 SYNOPSIS

Title:	Keeping in Touch with Youth as they Transition Through Type 1 Diabetes Care: A randomized control trial comparing the effectiveness of an eHealth text message-based intervention in conjunction with usual T1D care compared to usual care alone on diabetes self-efficacy
Study Description:	A multi-center, 1:1 randomized control trial with 6 sites (4 in Ontario and 2 in Quebec)
Objectives:	Primary Objective: Diabetes self-efficacy (SEDM) Secondary Objectives: Transition readiness (READDY), Barriers to Diabetes Adherence (BDA) Stigma subscale, HbA1c, healthcare utilization and cost of implementation Exploratory Objectives: embedded process evaluation
Endpoints:	Primary Endpoint: SEDM at 12 months Secondary Endpoints: READDY, BDA Stigma subscale, diabetes-related admissions and emergency department visits, HbA1c, cost of implementation data and LLM chatbot data. Exploratory Endpoints: qualitative and quantitative data from embedded process evaluation
Study Population:	234 (117 in each arm) adolescents with T1D preparing to transition to adult diabetes care and receiving care for T1D at participating pediatric centres in Ontario or Quebec; English or French speaking and possess their own mobile device that can send and receive SMS messages
Description of Study Intervention:	Text-message based algorithm that operates similar to a chatbot and will send SMS messages for T1D personalized support, education, resources and collection of outcome measures.
Study Duration:	21 months of recruitment and 12-month intervention period
Participant Duration:	12 months for each participant to complete the study

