8 STUDY ASSESSMENTS AND PROCEDURES

8.1 ASSESSMENTS

- **Questionnaires and patient-reported outcomes:** all the following will be sent as URLs via KiT intervention SMS that will link-out to web-based REDCap surveys:
 - KiT Demographic survey (diabetes care and self-management),

- READDY tool: transition readiness assessment for emerging adults with diabetes diagnosed in youth, administered at baseline, and 6 and 12 months after baseline
- SEDM: self-efficacy with diabetes self-management, administered at baseline, 6 and 12 months after baseline
- BDA Stigma subscale: type 1 diabetes stigma assessment subscale, administered at baseline, 6 and 12 months after baseline

- **Administrative data via OHIP or RAMQ number collection:** the following data will be collected via linking to administrative datasets via ICES in Ontario and Med-Echo and Régie de l'assurance maladie du Québec (RAMQ) databases in Quebec
 - Deprivation quintile
 - diabetes related ED visits and hospitalizations
 - HbA1c (in Ontario only)
- **Cost of implementation:** we will measure all relevant costs associated with the intervention and its implementation using study data. More specifically, costs will be collected in five broad categories: staff (e.g. salaries, fee for services), equipment (e.g. equipment/technology platform and depreciation costs, software costs, installation costs, and maintenance costs), communication (e.g. data transmission costs), administration (e.g. administration costs, supplies)

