8.5.3 ANALYSIS OF THE SECONDARY ENDPOINT(S)

For secondary outcomes, continuous data will be reported as means with SDs and between-arm differences in means will be calculated using Student's t-tests or non-parametric statistics. To account for repeated measures, secondary analysis will be conducted to calculate within (baseline, 6 months, 12 months) and between arm-differences to evaluate changes.

We will compare baseline adjusted self-reported mean HbA1c at 12 months between those in the intervention versus control arms. This will be done using linear regression to estimate the effect of the intervention on HbA1c.. The same Bayesian model as the primary analysis will be used. We will adjust for by sex and gender.

From the process evaluation, we will report metrics of user engagement by # of interested topics chosen by the participant, type of specific topics, proactive use of chatbot, response rate (%) to messages that query participants with a question or prompt requiring a SMS response, and proportion (%) of participant clicks on resource and educational links. Furthermore, qualitative observations made during the one-on-one interviews and surveys administered during the process evaluation will be analyzed using thematic analysis strategies guided by HAPA and the TAM, identifying key themes that demonstrate important contextual influences and practices related to the implementation and evaluation of the e-Health technologies in actual contexts of health care delivery. The findings of the qualitative data will be used to develop statements of the relationships between (a) key contextual factors (e.g., perceived needs, outcome expectancies, self-efficacy), (b) the mechanisms by which they affect the implementation of the e-Health interventions, and (c) the impact on the outcomes of the KiT intervention themselves (in Realist Evaluation these statements are referred to as “Context-Mechanism-Outcome Configurations” (43).

For the Coincidence Analysis, we will create individual case constructions for all trial participants that will triangulate intervention engagement data by intervention component with outcome data, using pathways informed by the semi-structured interviews. Where required, variable values will be converted to have categorical properties according to the definitions and criteria developed by the research team. CNA package in R will be used for data analysis.

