8.5.4 BASELINE DESCRIPTIVE STATISTICS

Summary statistics will be used to describe baseline characteristics and other outcomes of interest. Categorical endpoints will be summarized using proportions and frequencies. Continuous endpoints will be summarized using the mean, median, range or standard deviations. Subgroup summarization based on KiT intervention message frequency or other criteria will also be conducted.

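### READDY and stigma lack the baseline-adjusted model that SEDM and HbA1c get, and the any-of-three stigma definition hides partial improvement and does not fit the continuous-data test

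*Protocol*

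**What the plan says.** The secondary-endpoint table in Protocol section 3 reduces stigma to a binary state: "in our study, stigma will be defined as an affirmative response to at least one of three key items on this subscale". The synopsis (3.1) names the subscale with no cut: "Secondary Endpoints: READDY, BDA Stigma subscale, diabetes-related admissions and emergency department visits, HbA1c". So does section 8.1: "BDA Stigma subscale: type 1 diabetes stigma assessment subscale, administered at baseline, 6 and 12 months after baseline". READDY is collected at the same three times.

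Section 8.5.3 gives a general rule for secondary outcomes, written for continuous data: "between-arm differences in means will be calculated using Student's t-tests or non-parametric statistics". The next sentence deals with repeated measures: "secondary analysis will be conducted to calculate within (baseline, 6 months, 12 months) and between arm-differences to evaluate changes". Baseline adjustment is explicit for one secondary outcome only: "We will compare baseline adjusted self-reported mean HbA1c at 12 months between those in the intervention versus control arms". That analysis uses the primary model, which section 8.5.2 describes as a Bayesian mixed model with baseline SEDM, clustering by clinic, sex and gender.

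On categorical endpoints, section 8.5.4 says "Categorical endpoints will be summarized using proportions and frequencies". Section 6.2 stratifies randomisation by site.

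**The concern.** There are two linked weaknesses.

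1. **Method.** The primary outcome and HbA1c get a model that uses the baseline value and the site. READDY and stigma have the same baseline data and the same stratified randomisation, but get a two-sample comparison and an unspecified look at differences over time. No reason is given.

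2. **Endpoint.** The aim is to measure the intervention's impact over 12 months, but the stigma definition records only whether any endorsement remains. It also turns into a yes/no variable an outcome that the synopsis leaves as a subscale and that section 8.5.3 can handle only as a continuous score. Two readings of the endpoint stay open: score or proportion.

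At stake are precision on two patient-reported secondary outcomes and a choice of stigma endpoint that should be settled before the data are seen.

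**Working it through.** **1. The plan's own figure.** Section 8.3 gives power only for SEDM: more than 80% for a difference of 0.75 with 117 per arm and 20% loss. No SD is stated, so the figure cannot be reproduced. The loss step is consistent: 117 × 0.8 = 93.6, or about 93 per arm. At 93 per arm (two-sided 5% t-test), 80% power requires an SEDM SD of at most about 1.82. No power is claimed for READDY or stigma. The steps below use 93 per arm.

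**2. What the cut registers.** By the definition alone:

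| Items endorsed, baseline → 12 months | Status under the cut |
|---|---|
| 3 → 2, 3 → 1, 2 → 1 | no change |
| 3 → 0, 2 → 0, 1 → 0 | improved |

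Worsening from 1 to 2 or 3 items is likewise invisible.

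**3. Baseline adjustment for a score.** Let r be the correlation between the baseline and 12-month values (assumed), with equal variances at the two times.

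- Variance of the arm difference relative to an unadjusted 12-month comparison: 1 − r². At r = 0.4 this is 0.84 (16% less); at r = 0.6 it is 0.64 (36% less).
- Equivalent unadjusted sample: 93/0.84 ≈ 111 and 93/0.64 ≈ 145 per arm.
- If the repeated-measures sentence is read as a comparison of change scores, their relative variance is 2(1 − r): 1.20 at r = 0.4 and 0.80 at r = 0.6. The adjusted model is still better, by the factor (1 + r)/2: 0.70 and 0.80.

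**4. Cut versus item count.** Simulation of three correlated yes/no items at two times, 3,000 runs per setting (Monte Carlo error below 1 point). Assumptions: 93 per arm, latent correlation between items 0.5 and over time 0.6, a shift of 0.4 SD on every item, and linear models tested at two-sided 5%. Site, sex and gender were not simulated.

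| Item prevalence | Any-of-three rate, control / intervention | Power, cut | Cut + baseline | Count | Count + baseline | Fewer items endorsed but still counted as stigma |
|---|---|---|---|---|---|---|
| 20% | 39.0% / 23.3% | 65.0% | 70.5% | 69.6% | 77.0% | 24% |
| 35% | 59.3% / 41.3% | 68.8% | 76.0% | 79.4% | 87.0% | 38% |
| 50% | 74.9% / 58.6% | 66.7% | 72.6% | 82.1% | 90.0% | 51% |

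Gain from cut to count without baseline: 4.6, 10.6 and 15.4 points. With baseline: 6.5, 11.0 and 17.4 points. Adding baseline alone gains 5.5, 7.2 and 5.9 points for the cut, and 7.4, 7.6 and 7.9 for the count.

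**5. The cut as a plain comparison of proportions.** With assumed control rates of 40% to 80% and 93 per arm, power is 28–35% for a 10-point drop, 54–63% for 15 points and 79–85% for 20 points.

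**The case against.** The strongest defence is that little here is wrong. In a randomised comparison an unadjusted test is valid, and adjustment only buys precision. The any-of-three state is prespecified and easy to interpret. The subscale is supported by a cited study that cannot be consulted here, so whether that source justifies this cut is unknown. The protocol does not document how the subscale is scored or how well it responds to change. Stigma is one of several secondary outcomes, with no power claim, and the directional part of the hypotheses in section 8.2 does not name it. All of this stands. It argues for keeping the cut as a reported result and for treating the point as an improvement.

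A reader might also infer four stronger things that the document does not support:

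- *That the secondary analyses ignore baseline.* Section 8.5.3 plans within- and between-arm differences across baseline, 6 and 12 months. What is absent is a named baseline-adjusted model for READDY and stigma.
- *That stigma will have no between-arm comparison.* Section 3 states the objective as impact compared with usual care. A binary method may properly sit in an analysis plan that is not shown, and section 8.5.4 concerns mainly baseline description.
- *That READDY is also dichotomised, or that most of its responsiveness is lost.* The cut applies to stigma only.
- *That the cut discards 36% to 51% of the information.* Those figures come from φ(z)²/[p(1 − p)] for a normal score split at 50% to 80% prevalence. The protocol gives no score range or distribution for the subscale, so the three-item comparison is the more suitable guide.

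**Conclusion.** The point holds as a modest, nearly free improvement. Section 8.5.3 states a less precise method for READDY and stigma than for SEDM and HbA1c, with baseline data and site equally available. The stigma definition in section 3 counts improvement short of zero endorsements as no change, and it fits neither the continuous-data rule nor the uncut subscale in the synopsis.

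Baseline adjustment removes about 16% to 36% of the variance for correlations of 0.4 to 0.6. The item count adds about 5 to 15 points of power over the cut without baseline, and about 6 to 17 with it. Every one of these figures rests on assumed prevalences, correlations and effects. The simulation also assumes an equal shift on all three items, which suits the count. An effect confined to clearing the last endorsed item would favour the cut. The trial's primary conclusion is not affected.

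**What to change.** - **Section 8.5.3:** analyse 12-month READDY, and the BDA stigma score or 0–3 item count, with the model already planned for SEDM and HbA1c: baseline value of that instrument, site, sex and gender.
- **Section 8.5.3:** keep the any-of-three proportion as defined and compare it between arms with a binary model adjusted for baseline stigma status.
- **Sections 3 and 3.1:** describe the stigma endpoint in the same terms in both places, with both forms listed and the leading one named before the data are analysed.

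The cost is wording and one extra model per instrument. No new data are needed. A second stigma result must be reported, and retaining the proportion keeps the any-of-three result available as originally defined.
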